Upon entry in the clinical trial, the master study database (REDCap, described later in Section 16) will randomly allocated patients to one of the study arms (1:1) within site (1:1) using a computer generated random sequence. This will provide an allocation sequence for each site. Once a patient is enrolled and a database file in REDCap is initiated for that patient, he/she will be assigned electronically to one of the study arms.

Patient will be blind to the intervention but surgeon blinding will not be feasible due to the nature of the intervention. The study will involve a considerable number of surgeons in each site, which should compensate any potential bias of some of them in favor or against either approach.

e. Flow chart

Multi-center Study Protocol: Efficacy of Near Infrared Incisionless Fluorescent Cholangiography (NIFC) during Laparoscopic Cholecystectomy

[figure not shown]
Figure 1 shows the flow chart for the study, a multi-centered randomized controlled trial (RCT) 1:1 with two arms:

1. Control: WLI

A laparoscopic cholecystectomy will be performed using Xenon white light imaging (WLI) only.

2. Experimental: NIFC

A laparoscopic cholecystectomy will be performed using both white light imaging and near infrared light imaging with indocyanine green (ICG) intravenous dye.

9. Data collection and procedures

Data will be collected before, during and at the end of surgery; and one week after surgery.

a. Pre-Op data collection

i. Patient data

- Age
- Gender
- Weight
- Height
- BMI

ii. Patient clinical characteristics

- Liver disease
- Lithiasis
- Surgical status: elective/urgent/emergent

b. Intra-Op data collection

i. For NIFC arm only

- Time of ICC administration
- Was there any Adverse Reaction? If so, what happened and how was the patient treated?

ii. For both arms: PRIOR to dissection

- Categorize initial visualization
 - Amount of fat
 - Amount of inflammation
 - Presence of adhesions / scar tissue
- Remove the fat from the Calot's triangle area, retract the gallbladder and Hartmann's pouch
- Surgeon/Observer documents which extra-hepatic biliary structures are identified without doubt
- Start Dissection. Document the time hilar dissection was begun (baseline time)

iii. For both arms: AFTER dissection

- Surgeon/Observer documents which extra-hepatic biliary structures are identified without doubt
- Time to Clip: Document the time the Cystic Duct was clipped
- Volume of Bleeding
- Incidence of Bile Leakage

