- Incidence of Anatomic Anomalies of the extra-hepatic biliary system, including any Accessory Ducts
- Incidence of performing IOC
- Incidence of CBD stones
- Incidence of Conversion to open surgery
- Incidence of Bile Duct Injury (BDI)?

iv. For NIFC arm only

- PRIOR to and AFTER DISSECTION: Surgeon/Observer documents which extra-hepatic biliary structures are identified without doubt using the "Reflux Maneuver" during NIFC
- Was the "reflux maneuver" useful?
- Surgeon preference: Was NIFC helpful?

c. One-week Post-Op data collection (usual control after surgery)

- Length of hospital stay

- Readmission?
- Complications?
 - Adverse drug reactions
 - Hemorrhage
 - Bile leak
 - Bile duct injury
- Death?

10. Subject Selection

a. Inclusion Criteria

1. Patients of both genders
2. Minimum age: 18 years old
3. Spoken and written command of the language spoken in the country's center
4. Ability to understand and follow the study procedures and sign the informed consent

b. Exclusion Criteria

1. Known allergies to iodides
2. Known history of cholangitis, pancreatitis, CBDS's, coagulopathy
3. Known liver disease
4. Women who are pregnant or breastfeeding, or for whom possibility of pregnancy was not ruled out

11. Study Device

a. Indocyanine Green (ICG) Fluorescent Dye

The drug used in these studies to evaluate the extra-hepatic bile duct is indocyanine green (ICG) and the equipment uses a wavelength around 800 nm (32,33,34,35,36,37). ICG, a cyanine dye, has been used in various medical diagnostic procedures since its FDA approval in 1956 (38).

ICG is a fluorophore responding to near-infrared irradiation that absorbs light between 790 and 805 nm, and re-emits it with an excitation wavelength of 835 nm. When given intravenously, ICG binds to plasma proteins and becomes confined to the intravascular space [15]. It is then exclusively metabolized by the liver and excreted by the biliary system 15 to 20 minutes after administration. These properties, in conjunction with the absence of any native biological fluorescence within these wavelengths, make ICG an ideal agent for the acquisition of high-quality images of the biliary tract.

b. Equipment

KARL STORZ (Tuttlingen, Germany) has developed a laparoscopic fluorescence imaging system that is suitable for both near-infrared fluorescence and xenon

Multi-center Study Protocol: Efficacy of Near Infrared Incisionless Fluorescent Cholangiography (NIFC) during Laparoscopic Cholecystectomy

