c. Patient Randomization

Each surgeon will follow the standard laparoscopic surgical protocol of his/her center, and will comply with the following additional steps according to which arm of the study the patient is assigned:

i. Control arm (WLI only) procedures

1. After inserting the scope in the abdominal cavity, once other standard operatory procedures (e.g., taking down adhesions if necessary, or releasing scar tissue) are completed using white light imaging (WLI) only, the Researcher will record the time when Calot's triangle is first visualized. From this moment on, the surgery will be recorded.
2. After removing the fat from the gallbladder area, lifting the gallbladder over the liver, and grabbing the Hartman's pouch to visualize the Calot's triangle, but PRIOR TO DISSECTION, the Researcher will determine what extra-hepatic biliary structures can be specifically identified. Of note: because one of the goals of the Study is to evaluate NIFC as a teaching tool, residents and juniors should record what structures they were able to identify by themselves before any intervention of the attendant surgeon.
3. Then, AFTER DISSECTION, a similar assessment of what extra-hepatic biliary structures can be specifically identified using WLI only will be performed.
4. Anatomic anomalies of the biliary system will be documented on the case form and if an anatomic variation is found, a snap shot photo will be taken in addition to the video.
5. Immediately before clipping or proceeding with open surgery, the total time from Step 1 will be recorded, known herein as the "Time to Clip";

6. Before leaving the operation room, all participant surgeons and observers will complete the Intra-Operative Case Report Form (Appendices D and E, respectively).

ii. Experimental arm (NIFC) procedures

1. Patient randomized to the experimental arm, at least 45 mins before surgery, will receive a weight-scaled dose of indocyanine green (0.05 mg/kg) by IV and the time of administration and any adverse reactions will be recorded.
2. After inserting the scope in the abdominal cavity, once other standard operatory procedures (e.g., taking down adhesions if necessary, or releasing scar tissue) are completed using white light imaging (WLI) only, the Researcher will record the time when the Calot's triangle is first visualized. From this moment on, the surgery will be recorded.

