If necessary, and if agreed upon by KARL STORZ, the enrollment period will be extended to reach the proposed 1,000 patients.

b. Approaches to Missing Data

We do not expect missing data for the main outcome as this information will be collected immediately after or during the surgery. Some of the secondary outcomes will be collected in a very short follow up period (7-10 days); we have however considered the alternative of phone calls to recover information in those patients not attending to clinic after surgery. Missing data on covariates are not expected either, as they are routine laboratory tests and studies.

15. Safety and Adverse Effects

a. Risks and Benefits

The dye may cause a feeling of warmth for several minutes following the injection. It may cause a change in the color of the stool (green). Uncommon allergic reactions include itchy skin and hives. Rare more severe allergic reactions such as wheezing, difficulty breathing, and low blood pressure may occur.

There is no personal benefit by participating in this research study. The increased visualization of the extra-hepatobiliary anatomy may aid the surgeon.

The knowledge to be gained from this research may be beneficial for other patients, society or science.

b. Potential Risks

Multi-center Study Protocol: Efficacy of Near Infrared Incisionless Fluorescent Cholangiography (NIFC) during Laparoscopic Cholecystectomy

Potential risks are similar to routine laparoscopic cholecystectomy, including possible bile duct injury, bleeding, and/or conversion to open surgery.

Drug related adverse complications may be due to allergic reactions.

c. Procedure to Minimize Risk

Administration and dose of ICG will be confirmed and performed only by trained medical personnel. During the surgical procedure, the patient will be closely monitored by the operating room staff.

d. Potential Benefits

The increased visualization of the extra-hepatic biliary anatomy may aid the surgeon.

The knowledge to be gained from this research may be beneficial for other patients, society or science.

16. Data Handling and Record keeping (REDCap)

a. Overview

The medical and research information recorded about the patient for this research will be used within the Institution and/or disclosed outside the Institution as part of this multi-center study. The procedure done solely for this research study may be placed in the medical record to indicate the patient's participation in this study.

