Near Infrared Incisionless Fluorescent Cholangiography (NIFC)
INTRA-OPERATIVE CASE REPORT FORM - PERFORMING SURGEON

INSTITUTION: _____ PATIENT ID: _____ PROCEDURE DATE: _____

SURGEON NAME: _____
(PRINT) _____ (SIGNATURE) _____

ACADEMIC TITLE: _____ Years in practice: _____ Approx. #Lap Choles Performed: _____

STUDY ARM: **WLI** (STD mode on light source only) **NIFC** (using both STD and ICG modes)

1. For NIFC group only:

- Time of ICG Administration: _____ AM / PM
- Was there an Adverse Reaction to the ICG? Yes No
If Yes, how was it detected? _____
If Yes, how was it managed? _____

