<hr/> 
1. Length of hospital stay: _____ (days)
 
2. Was patient readmitted: No  Yes  If Yes, complete the following:
 
Days after discharge: _____ (NOTE: Day of Surgery is Day "0")Reason for readmission: _____Treatment administered: _____Length of stay: _____ (days) 
3. Death (30 d): No  Yes  If Yes, cause of death: _____
 
4. Complications: No  If No, you have completed this form. Yes  If Yes, please continue...
 
Indocyanine green drug reactions: No  If No, skip to surgical complications. Yes  If Yes, continue
Flushing? No  Yes  If yes, please complete:
Treatment required? No  Yes If Yes, what treatment: _____Urticaria? No  Yes  If yes, please complete:
Treatment required? No  Yes If Yes, what treatment: _____Other possible drug reaction? No  Yes  If Yes, please complete:
Describe: _____Onset (day of surgery is "0"): _____Duration (Hours): _____Treatment required? No  Yes If Yes, what treatment: _____ <hr/> 
MULTICENTER TRIAL
 
Page 1 of 2
 
POSTOP-CRF v1.0
		

Near Infrared Incisionless Fluorescent Cholangiography (NIFC)

2

POST-OPERATIVE FORM

b. Hemorrhage? No Yes If Yes, please complete:

- i. ... requiring transfusion? No Yes
- ii. ... requiring re-operation? No Yes
- iii. ... requiring longer hospitalization? No Yes

c. Intra-abdominal pain in right upper quadrant? No Yes

d. Bile leak (without bile duct injury)? No Yes If Yes, please complete:

- i. ... requiring percutaneous drainage? No Yes
- ii. ... requiring reoperation? No Yes
- iii. ... treated with percutaneous drainage only? No Yes
- iv. ... treated with transpapillary stent? No Yes
- v. ... treated with percutaneous drainage and transpapillary stent? No Yes

vi. Source of leak:

1. cystic duct stump leak? No Yes
2. liver bed? No Yes
3. never determined? No Yes

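### On the post-operative form the ICG-reaction questions sit behind a general complications question, so mild late dye reactions may be under-counted

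*Combined protocol and SAP*

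**What the plan says.** Dye reactions are collected in two places.

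**During surgery.** Section 9.b.i lists, for the NIFC arm, "Was there any Adverse Reaction? If so, what happened and how was the patient treated". Section 12.c.ii step 1 also requires reactions to be recorded when the dye is given. Item 1 of the surgeon's form (Appendix d) puts this into practice for the NIFC group: "Was there an Adverse Reaction to the ICG? Yes No". It follows up with how the reaction was detected and managed. Section 12.c.ii step 7 fixes when the form is filled in: "Before leaving the operation room, all participant surgeons and observers will complete the Intra-Operative Case Report Form".

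**At follow-up.** Section 9.c lists "Adverse drug reactions" as the first entry under complications at one week. Section 12.d places the post-operative form (Appendix f) at the standard visit, typically 7-10 days after surgery. Item 4 of that form asks first about complications in general. A negative answer leads to "If No, you have completed this form". Only after a positive answer does the completer reach item 4.a, "Indocyanine green drug reactions: No", whose negative branch reads "If No, skip to surgical complications". Its positive branch opens separate questions on flushing, urticaria and any other possible drug reaction.

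**The concern.** Dye effects are asked about specifically only after someone has already decided that the patient had a complication. Section 15.a describes mostly mild effects: "The dye may cause a feeling of warmth for several minutes following the injection", a change in stool colour, itching and hives, with severe allergic reactions described as rare. The other entries under item 4 include hemorrhage, bile leak and bile duct injury. Next to these, a short-lived rash after discharge is the kind of event that a completer may not think of as a complication, or may never ask about.

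At stake is the completeness of the one-week drug-reaction data that Section 9.c asks for. The dye is the added drug exposure in the NIFC arm, given to about 500 patients under the allocation assumed in Section 13.a. If the specific question is not put to all of them, a late-reaction count has the dosed patients as its denominator, but only a self-selected part of them was asked item by item.

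**Working it through.** No arithmetic applies. The plan states no dye-reaction rate, and no figure in it depends on this skip. The check is to follow a reaction through the forms by time and severity.

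1. **Warmth within minutes of injection.** The dye is given at least 45 minutes before surgery (Section 12.c.ii step 1), and the surgeon's form is completed at the end of the operation. The effect falls inside the window of the unfiltered intra-operative item, so it is captured.
2. **Any reaction noticed between injection and the end of surgery.** Same route, asked for every NIFC patient. Captured.
3. **A severe reaction after the operating room.** It would probably be called a complication. If it led to readmission, item 2 of the post-operative form, which precedes the complications question, asks for the reason. Probably captured.
4. **A mild later reaction, known to the completer and regarded as a complication.** Item 4 is answered Yes and item 4.a is reached. Captured.
5. **A mild later reaction, not volunteered or not regarded as a complication.** Item 4 is answered No and the form ends. Not captured.

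Only the fifth path is a gap. Four features of the documents make it worth closing:

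- Under other possible drug reactions, item 4.a asks for day of onset, counting the day of surgery as zero. The form therefore allows for reactions that begin after surgery.
- Both intra-operative forms (Appendices d and e) have a study-arm box. The post-operative form has none, so nothing on it tells the completer that this patient received the dye.
- The observer's form (Appendix e) has no dye-reaction item, and the list of appendices shows no separate adverse-event form. After the surgeon's form is closed, item 4.a is the only dedicated field.
- Section 14.b allows telephone contact for patients who miss the visit. If the form is followed on the call, a general No ends the questions there too.

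The documents give no time of onset for itching or hives, so they do not show how many reactions, if any, would follow the fifth path.

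**The case against.** The strongest reply is that the form already treats dye reactions as complications. The question in item 4 is not restricted to surgical events. Drug reactions are its first sub-item, and the instruction in item 4.a separates them from surgical complications. Section 9.c groups them the same way. A completer who knows of a reaction and follows the documents answers Yes. A ticked No is also a recorded negative to a question that includes drug reactions, not a blank. All of this stands. What remains is a completer who reads the word narrowly, or a patient who is never prompted about specific symptoms.

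The reply also holds for stronger conclusions that a reader might draw:

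- *That dye reactions in general go unrecorded.* They do not. The period from injection to the end of surgery has its own unfiltered question, and the one effect whose timing Section 15.a describes falls within it.
- *That the dye's safety would be overstated.* The documents do not show this. Dye reactions are not a primary or secondary endpoint (Section 5), Section 13.b plans no analysis of them, and any shortfall has unknown size.
- *That the precision lost can be calculated by assuming a complication rate and counting only patients past item 4 as asked.* This would rest on a rate the plan does not give. It would also ignore both the recorded No and the intra-operative item asked of every NIFC patient.
- *That right-upper-quadrant pain, also behind the same question, should be moved.* Section 15.a does not describe it as a dye effect, so this argument does not reach it.

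**Conclusion.** The point holds in a limited form. Mild reactions that start or are first reported after the surgeon's form is completed, up to the 7-10 day visit, depend on a general question and may be under-counted. The direction is towards too few. The amount cannot be derived from the documents. No listed endpoint, test or sample-size figure changes.

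The conclusion assumes that the electronic form in REDCap follows the printed skip instruction; its branching is not shown. It also assumes that some completers will read the general question narrowly or will not prompt for symptoms, which the documents neither confirm nor exclude. On that footing this is a cheap improvement, not a flaw that threatens the trial's conclusions.

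**What to change.** - In Appendix f and in REDCap, place item 4.a (flushing, urticaria, other possible drug reaction) before the general complications question.
- Make it mandatory for every NIFC patient, with an explicit Yes or No for each part. The arm is already held in REDCap and can drive the branching; the paper form needs a study-arm box like the one on the intra-operative forms.
- State in Section 13.b that ICG reactions will be reported over all dosed patients, combining the intra-operative and post-operative items.

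The cost is one change to the form and its branching, and slightly more form time at a visit or call that already takes place. More minor reactions will be counted in the NIFC arm, and the report should say that they were specifically asked about. Section 8.d keeps patients blind to their arm, so the questions are best asked by symptom, without naming the dye.

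### Possible drug reactions are not collected during surgery in the WLI arm and are gated out for it afterwards, so the NIFC rate of non-specific signs has no concurrent background

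*Combined protocol and SAP*

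**What the plan says.** **During surgery.** Section 9.b.i, under a heading restricted to the NIFC arm, asks "Was there any Adverse Reaction? If so, what happened and how was the patient treated". Section 12.c.ii step 1 has reactions to the injection recorded in the experimental arm; the control steps in 12.c.i have no counterpart. Item 1 of the surgeon form (Appendix d), also restricted to NIFC, asks "Was there an Adverse Reaction to the ICG". The observer form (Appendix e) has no reaction item.

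**After surgery.** Section 9.c lists "Adverse drug reactions" among the one-week complications, with no arm label. Section 12.d has the post-operative form (Appendix f) completed at the follow-up visit, without restriction by arm. Item 4 of that form has two gates in sequence. The complications question comes first, and a No ends the form: "If No, you have completed this form". The next question is headed "Indocyanine green drug reactions: No", and a No there carries the instruction "If No, skip to surgical complications". Flushing, urticaria and a general field for other possible drug reactions all sit under this second gate.

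**Expected signs.** Section 15.a lists warmth, itching, hives, wheezing, breathing difficulty and low blood pressure as possible effects of the dye.

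**Analysis.** Drug reactions are not among the endpoints in Section 5, and Section 13.b plans no comparison of them.

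**The concern.** The signs in Section 15.a are not specific to ICG. I assume that some of them can occur around an operation for other reasons; the documents give no background rate. When hives or hypotension appear in an NIFC patient, someone has to decide whether the dye was the cause. Section 8.d says that surgeons cannot be blinded, so staff who know the arm make that decision.

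A randomised control arm is the natural source of a background rate, and the trial already has one. The forms do not use it. At stake is what the trial can say about the safety of the dye: it can report how many reactions staff attributed to ICG, but not whether these signs were more common than in similar patients operated on without it.

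**Working it through.** **Step 1. Trace each reaction field by arm.**

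| Place | NIFC | WLI |
|---|---|---|
| 9.b.i; 12.c.ii step 1; surgeon form item 1 | Asked | Not asked |
| Observer form | No item | No item |
| Post-operative form, flushing and urticaria | Reached after Yes, Yes | Skipped: the correct answer to the ICG gate is No |
| Post-operative form, other possible drug reaction | Reached after Yes, Yes | Skipped, same reason |
| Post-operative form, remaining complications (hemorrhage, right upper quadrant pain, bile leak, bile duct injury) | Asked after Yes to complications | Same, but none is a drug reaction |
| Post-operative form, free text for readmission and cause of death | Available | Available, but reaches severe events only, and not systematically |

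A WLI patient with hives therefore has no structured field at any time point.

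**Step 2. Can timing replace a comparator?** Only in part. The injection time is recorded, and Section 15.a expects warmth within minutes of it. But the surgeon form has no field for the time of a reaction. The post-operative form asks for onset only for other drug reactions, by day, and not for flushing or urticaria.

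**Step 3. What the NIFC arm alone can say.** The plan gives no figure for drug reactions to reproduce. I take n = 500 per arm from Section 13.a; the event counts below are hypothetical. The exact (Clopper-Pearson) 95% limits for k events in n are:

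- lower = Beta quantile at 0.025 with parameters (k, n − k + 1)
- upper = Beta quantile at 0.975 with parameters (k + 1, n − k)
- for k = 0, upper = 1 − 0.025^(1/500) = 0.735%

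| Events in NIFC | Rate | Exact 95% interval |
|---|---|---|
| 0/500 | 0% | 0 to 0.74% |
| 5/500 | 1.0% | 0.33% to 2.32% |
| 10/500 | 2.0% | 0.96% to 3.65% |

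These intervals describe ICG-attributed reactions adequately. They say nothing about how many of the same signs would have occurred without ICG.

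**Step 4. What a both-arm item would add.** Suppose the true rate of these signs is the same in both arms: an assumed 1% (500 × 0.01 = 5 per arm) or 2% (500 × 0.02 = 10 per arm). With Wilson limits l and u for each arm, the Newcombe limits for the difference at equal observed rates p are ± √[(p − l)² + (u − p)²].

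- 5 against 5: l = 0.428%, u = 2.319%; √(0.572² + 1.319²) = 1.44. The difference is 0, with limits −1.44 to +1.44 percentage points.
- 10 against 10: l = 1.090%, u = 3.642%; √(0.910² + 1.642²) = 1.88. The difference is 0, with limits −1.88 to +1.88 percentage points.

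**Step 5. Power of that comparison.** Two-sided Fisher exact test at 5%, 500 per arm, assumed rates:

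| NIFC against WLI | Power |
|---|---|
| 2% against 1% | 18% |
| 3% against 1% | 56% |
| 4% against 1% | 85% |

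The comparison could bound a large excess but could not reliably detect a doubling from 1%. It belongs in a descriptive table.

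**The case against.** The strongest reply is that nothing planned is wrong. Only patients given ICG can react to ICG, so asking them alone gives the right denominator. Reactions are not an endpoint and no test of them is planned. Section 9.c may simply abbreviate the ICG item, since Section 11.a says "The drug used in these studies to evaluate the extra-hepatic bile duct is indocyanine green (ICG"; on that reading, protocol and form agree and only a label is missing. All of this stands. It is why the point is minor and why the one-arm rate is not in dispute. It does not settle attribution: whether hives in an NIFC patient are an ICG reaction is the judgement that a control rate would inform.

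A reader might go further and infer that WLI reactions are zero by construction, or that the trial will show a false excess in NIFC. The documents do not support either reading. During surgery, WLI data are not collected, which is different from zero. After surgery, the No follows from the label and skip rule, not from an arm restriction, so a Yes entered against the label is possible. A false excess would need three things that the documents do not contain: a known background rate, staff who attribute every such event to the dye, and an analyst who counts uncollected WLI data as zero.

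It can also be objected that asking about suspected drug reactions in both arms would bring the attribution problem back, because unattributed hypotension or wheezing in WLI would still be missed. That is correct, and the remedy has to be based on signs.

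**Conclusion.** The point holds as a minor data-collection gap. In the WLI arm, possible drug reactions are not collected during surgery and are gated out of the post-operative form. The trial therefore cannot set the NIFC frequency of the Section 15.a signs against a concurrent randomised background, and staff who know the arm make the attribution.

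No endpoint, test or sample-size statement is affected. The size of the gap cannot be computed from the documents, because they give no background rate; the rates of 1% to 4% above are assumptions that show scale only. If the background is in fact negligible, little is lost. That the signs can have other causes around surgery is also an assumption. The routing of the forms is not: it can be read directly from them.

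**What to change.** 1. On the surgeon form, and on the post-operative form before item 4, ask in both arms a checklist of signs that does not require suspicion of a drug cause: flushing or warmth; itching or urticaria; wheezing or difficulty breathing; hypotension requiring treatment; other. Record onset date and time, and treatment. Placing it before item 4 means that a No to complications cannot bypass it.
2. Record attribution to ICG as a separate question, in NIFC only.
3. Add to Section 13.b a descriptive table: the proportion of patients with any listed sign by arm, each patient counted once across the forms, with the risk difference and Newcombe 95% interval; and the ICG-attributed proportion among patients given ICG, with an exact 95% interval.

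If the sponsor wants ICG reactions only, label the 9.c item as NIFC only and descriptive, and make no between-arm statement about reactions.

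**Cost.** One item on each of two forms and one table; the alternative costs a label. Limits remain: power is low (about 18% for an assumed 2% against 1%), intra-operative reporters stay unblinded, and the control steps list no sham injection, so warmth linked to the injection has no matched control window.
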